### **8.3.3. Concomitant Medications**

Concomitant medications will be coded using the World Health Organization (WHO) Drug Dictionary (Enhanced B2, March, 2016) and summarized to the therapeutic drug class (Anatomical Therapeutic Chemical (ATC) 4 classification) and preferred name.

### **8.3.4. Clinical Laboratory Data**

All hematology and chemistry laboratory assessments were performed by local laboratories.

The following protocol-specified clinical laboratory findings will be summarized using descriptive statistics by dose level.

1. Hematology:
  - a. Hemoglobin
  - b. Neutrophils (absolute and %)
  - c. Platelets
  - d. Reticulocyte %
  - e. WBC
2. Chemistry and Liver Function Tests:
  - a. Alkaline phosphatase
  - b. ALT
  - c. AST
  - d. Potassium
  - e. Indirect bilirubin
  - f. Total bilirubin
  - g. Serum Erythropoietin

Change from baseline and the percent change from baseline will be summarized for the above laboratory results. Analyte units will be converted to SI units.

Participant listings of laboratory data will include a separate listing for clinically significant laboratory results. Urinalysis, coagulation and pregnancy results will be listed only.

### **8.3.5. Vital Signs and Physical Exam**

Part A vital signs and physical exam data will be listed only.

Part B vital signs, including systolic and diastolic blood pressure, heart rate, and weight will be summarized using continuous descriptive statistics at each visit and time point by dose level. Change from baseline will also be summarized for each post-baseline visit.

### **8.3.6. 12-Lead Electrocardiogram**

Heart rate, PR interval, QRS interval, QT interval, RR interval, and QTcF (Fridericia's) interval will be summarized along with the change from baseline using descriptive statistics at each visit in Part B. The average of the 3 ECGs collected will be used in the summary tables.

Additionally, in both Part A and Part B, the number and percentage of participants with QTcF  $\leq$  450 ms,  $>450$  ms to  $\leq 480$  ms,  $>480$  ms to  $\leq 500$  ms, and  $>500$  ms at baseline and as the maximum post-baseline measurement will be summarized. The number and percentage of participants with maximum increase from baseline where increase in QTcF  $\leq$  30 ms,  $> 30$  ms to 60 ms and  $> 60$  ms also will be summarized. If the QTcF interval was not collected, the interval will be calculated using the following formula:

$$\text{QTcF} = \text{QT} / (60/\text{HR})^{1/3}$$

## **9. PROTOCOL DEVIATIONS**

Protocol deviations as assessed by the study team will be displayed in a data listing and sorted by treatment group, subject number, and then by date (where applicable) within each subject number. The type of deviation along with a description and any additional comments about the deviation will be listed.

## **10. CHANGES IN THE PLANNED ANALYSES**

The secondary endpoint, proportion of days with SCD symptom exacerbation during the first 24 weeks of treatment, will not be summarized. The definition for this variable is not defined at the time of the analysis.

## 11. TABLES, FIGURES, AND LISTINGS

Key planned summary tables and listings are provided below. Additional listings and tables may be included in final CSR and table/listing numbers may change.

### 11.1. Tables Part A

Item	Title
Table 14.1.1.a	Demographics and Baseline Characteristics
Table 14.1.2.a	Baseline Sickle Cell Disease Characteristics
Table 14.1.3.a	Other Medical History
Table 14.1.4.a	Participant Follow-up and Termination from Study
Table 14.1.5.a	Concomitant Medications
Table 14.3.1.1.a	Overview of Treatment-Emergent Adverse Events and Serious Adverse Events
Table 14.3.1.2.a	Treatment-Emergent Adverse Events by System Organ Class, Preferred Term and Maximum Severity
Table 14.3.2.1.a	Summary of Hematology and Change from Baseline
Table 14.3.2.2.a	Summary of Serum Chemistry and Change from Baseline
Table 14.3.2.3.a	Summary of Liver Function Tests and Change from Baseline
Table 14.3.3.a	Corrected QT Interval (Fridericia) Maximum Post-Baseline and Maximum Increase from Baseline Categories

## 11.2. Listings Part A

Item	Title
Listing 16.2.1.a	Eligibility and Enrollment for Screen Failures
Listing 16.2.2.a	Protocol Deviations for Safety Population
Listing 16.2.3.a	Demographics for Safety Population
Listing 16.2.4.a	Baseline Characteristics for Safety Population
Listing 16.2.5.a	Sickle Cell Disease History for Safety Population
Listing 16.2.6.a	Sickle Cell Disease Complications for Safety Population
Listing 16.2.7.a	Participant Follow-Up and Termination from Study for Safety Population
Listing 16.2.8.a	Prior and Concomitant Medications for Safety Population
Listing 16.2.9.a	Adverse Events for Safety Population
Listing 16.2.10.a	Study Drug Administration for Safety Population
Listing 16.2.11.1.a	Clinically Significant Laboratory Results for Safety Population
Listing 16.2.11.2.a	Coagulation Results for Safety Population
Listing 16.2.11.3.a	Urinalysis Results for Safety Population
Listing 16.2.11.4.a	Pregnancy Results for Safety Population
Listing 16.2.12.a	Vital Signs for Safety Population
Listing 16.2.13.a	Electrocardiogram for Safety Population
Listing 16.2.14.a	Physical Examinations for Safety Population

### 11.3. Tables Part B

Item	Title
Table 14.1.1.b	Eligibility and Enrollment
Table 14.1.2.b	Demographics and Baseline Characteristics
Table 14.1.3.b	Baseline Sickle Cell Disease Characteristics
Table 14.1.4.b	Other Medical History
Table 14.1.5.b	Participant Follow-up and Termination from Study
Table 14.1.6.b	Concomitant Medications
Table 14.1.7.b	Study Drug Exposure
Table 14.2.1.1.b	Summary of Hemoglobin and Measures of Hemolysis
Table 14.2.1.2.b	Hemoglobin Responders
Table 14.2.2.b	Summary of TCD Velocity and Change from Baseline
Table 14.2.3.b	Summary of Sickle Cell Disease Measure Total Symptom Score and Change from Baseline
Table 14.3.1.1.b	Overview of Treatment-Emergent Adverse Events and Serious Adverse Events
Table 14.3.1.2.1.b	Treatment-Emergent Adverse Events by System Organ Class, Preferred Term and Maximum Severity
Table 14.3.1.2.2.b	SCD Related Treatment-Emergent Adverse Events by System Organ Class, Preferred Term and Maximum Severity
Table 14.3.1.3.1.b	Treatment-Emergent Adverse Events Related to Study Drug by System Organ Class, Preferred Term and Maximum Severity
Table 14.3.1.3.2.b	SCD Related Treatment-Emergent Adverse Events Related to Study Drug by System Organ Class, Preferred Term and Maximum Severity
Table 14.3.1.4.b	Treatment-Emergent Adverse Events by Preferred Term
Table 14.3.1.5.b	Treatment-Emergent Adverse Events Related to Study Drug by Preferred Term
Table 14.3.1.6.1.b	Serious Adverse Events by System Organ Class and Preferred Term and Maximum Severity
Table 14.3.1.6.2.b	SCD Related Serious Adverse Events by System Organ Class and Preferred Term and Maximum Severity
Table 14.3.2.1.b	Summary of Hematology and Change from Baseline

Item	Title
Table 14.3.2.2.b	Summary of Serum Chemistry and Change from Baseline
Table 14.3.2.3.b	Summary of Liver Function Tests and Change from Baseline
Table 14.3.2.4.b	Summary of Serum Erythropoietin and Change from Baseline
Table 14.3.3.b	Summary of Vital Sign and Weight
Table 14.3.4.1.b	Summary of Electrocardiograms
Table 14.3.4.2.b	Corrected QT Interval (Fridericia) Maximum Post-Baseline and Maximum Increase from Baseline Categories

## 11.4. Listings Part B

Item	Title
Listing 16.2.1.b	Eligibility and Enrollment for Screen Failures
Listing 16.2.2.b	Protocol Deviations for Safety Population
Listing 16.2.3.b	Demographics for Safety Population
Listing 16.2.4.b	Baseline Characteristics for Safety Population
Listing 16.2.5.b	Sickle Cell Disease History for Safety Population
Listing 16.2.6.b	Sickle Cell Disease Complications for Safety Population
Listing 16.2.7.b	Hu History for Safety Population
Listing 16.2.8.1.b	Adverse Events for Safety Population
Listing 16.2.8.2. b	Serious Adverse Events for Safety Population
Listing 16.2.9.1.b	Clinically Significant Laboratory Results for Safety Population
Listing 16.2.9.2.b	Coagulation Results for Safety Population
Listing 16.2.9.3.b	Urinalysis Results for Safety Population
Listing 16.2.9.4.b	Pregnancy Results for Safety Population
Listing 16.2.9.5.b	Pregnancy Results for Safety Population

## 1. GLOSSARY OF ABBREVIATIONS

Abbreviation	Description
AE	Adverse Event
ATC	Anatomical Therapeutic Chemical
BMI	Body Mass Index
CRF	Case Report Form
Cmin	Trough Concentration
Cmax	Maximum Concentration
CTCAE	Common Terminology Criteria for Adverse Events
HU	Hydroxyurea
ICH	International Conference on Harmonisation
MedDRA	Medical Dictionary for Regulatory Activities
NCI	National Cancer Institute
PT	Preferred Term
RBC	Red Blood Cells
SAE	Serious Adverse Event
SAP	Statistical Analysis Plan
SCD	Sickle Cell Disease
SD	Standard Deviation
SOC	System Organ Class
TAMM	Time-Averaged Mean of the Maximum
TCD	Transcranial Doppler
TEAE	Treatment-Emergent Adverse Event
WHO	World Health Organization

## 2. INTRODUCTION AND STUDY OVERVIEW

The purpose of this statistical analysis plan (SAP) is to describe the planned analyses of final data from GBT440-007 Part C.

Where applicable, the statistical analysis methods presented in this document supersede the statistical analysis methods described in the study protocol.

### Study Overview:

GBT440-007 is a multicenter, open-label study to evaluate the safety, PK and efficacy of voxelotor in pediatric subjects with SCD.

This study consists of 4 parts, Part A, Part B, Part C and Part D. The planned analysis of the final data from Part C (ages 4 to 17 years) is described in this SAP.

Part C assesses the safety, tolerability and PK, as well as the hematological effects and the effect on transcranial doppler (TCD) flow velocity of voxelotor in pediatric subjects with SCD who are 4 to 17 years of age.

Up to 50 pediatric subjects will be enrolled in Part C.

- At least 30 subjects must have a TCD velocity  $\geq 140$  and  $< 200$  cm/sec by nonimaging TCD ( $\geq 125$  and  $< 185$  cm/sec by imaging transcranial Doppler [TCDi]) upon Screening AND
- At least 20 subjects must be between 4 to 11 years of age

To further characterize a potential effect on TCD data for those subjects who have a TCD velocity  $\geq 140$  and  $< 170$  cm/sec by nonimaging TCD ( $\geq 125$  and  $< 155$  cm/sec by TCDi) upon screening, approximately 20 subjects may be added with a TCD velocity that falls within this range, depending on the emerging data. In this event, Part C will contain up to 70 pediatric subjects.

### 2.1. Objectives

### 2.2. Part C (Multiple Dose)

#### 2.2.1. Primary Objective

- To evaluate the effect of voxelotor on cerebral hemodynamics in pediatric subjects with SCD with elevated or conditional TCD flow velocity as assessed by TCD ultrasonography

#### 2.2.2. Secondary Objective

- To evaluate the effect of voxelotor on clinical measures of anemia and hemolysis
- To characterize the PK of voxelotor in plasma, whole blood and RBCs following multiple doses in pediatric subjects with SCD

- To evaluate the safety and tolerability of voxelotor following multiple doses in pediatric subjects with SCD
- To evaluate the proportion of subjects with normal TCD flow velocity (< 170 cm/sec by nonimaging TCD or < 155 cm/sec by TCDi) at 48 weeks
- To evaluate the effect of voxelotor on the incidence of stroke and vaso-occlusive crisis (VOC)

### 3. ENDPOINTS

#### 3.1. Endpoints for Part C

##### 3.1.1. Primary Endpoint

- Change from baseline to 48 weeks in cerebral blood flow as measured by the TAMM TCD velocity

##### 3.1.2. Secondary Endpoints

- Change from baseline to Weeks 24 and 48 in Hb, LDH, indirect bilirubin, and reticulocyte count
- Change from baseline to 24 weeks in cerebral blood flow as measured by the TAMM TCD velocity
- Time to initial Hb response, defined as change from baseline in Hb  $> 1\text{ g/dL}$
- Whole blood and plasma voxelotor PK ( $C_{\min}$ ,  $C_{\max}$ , AUC), plasma  $t_{1/2}$ , and percent Hb occupancy
- Proportion of subjects with normal TCD flow velocity ( $< 170 \text{ cm/sec}$  by nonimaging TCD or  $< 155 \text{ cm/sec}$  by TCDi) at 48 weeks
- Incidence of stroke and VOC during the study

##### 3.1.3. Safety Endpoints

- TEAEs and SAEs
- Clinical laboratory tests, vital signs, and ECGs

### 4. DEFINITIONS AND TERMINOLOGY

#### Study Day

Study Day is defined relative to initiation of treatment, i.e., Day 1. Thus, the study day of an event is calculated as:

$$\text{Study Day} = \text{event date} - \text{Day 1 date} + 1.$$

#### Study Visit

Study Visit is the nominal visit as recorded on the CRF.

#### Baseline

For all endpoints where both Screening and Day 1 pre-dose assessments are collected, baseline is defined as average of all assessments prior to the first dose. If there is an unscheduled visit prior to first dose, this unscheduled assessment will also be included in the baseline calculation.

## Change from Baseline

Change from baseline to follow-up visit will be calculated as the baseline measurement subtracted from the follow-up measurement for all assessments. Percent change from baseline values to post-baseline values will be calculated using the following formula where applicable:

$$([post-baseline value - baseline value] / baseline value) \times 100\%$$

## Exposure to Study Drug

Duration of exposure to study drug is defined as the number of weeks from Day 1 to the last date of dosing of Study drug. The derivation is as follows:

$$(\text{Last dose date} - \text{First dose date} + 1)/7$$

Actual exposure to study drug is defined as the number of weeks from Day 1 to the last date of dosing of Study drug which excludes days where treatment was entirely missed or intermittently stopped as recorded in the CRF. The derivation is as follows:

$$(\text{Last dose date} - \text{First dose date} - \text{Number of days study drug was not taken} + 1)/7$$

## Prior Medications

Prior medications are those medications taken prior to the initiation of study drug.

## Concomitant Medications

Concomitant medications are those medications taken on or after the initiation of study drug. This definition includes medications started prior to the initiation of study drug, but continuing concurrently with study drug.

RBC transfusions are collected as concomitant medications.

## Hemoglobin Response

An Hb response is defined as an increase in Hb  $> 1$  g/dL from Baseline to each week of interest.

## Annualized Incidence Rate

Annualized incidence rate = (total number of events recorded over the treatment period) / (total person years)

Total person-years = sum of subject treatment period in years, which covers the time from first dose to last dose

## Treatment-emergent Adverse Event

A treatment-emergent adverse event (TEAE) is defined as an AE that emerges on or after initiation of study drug (having been absent pre-treatment), or an AE that existed pre-treatment and worsened on treatment (relative to the pre-treatment state) through 28 days after study drug discontinuation. AEs occurring on Day 1 are assumed to be treatment-emergent.

## **5. GENERAL STATISTICAL CONSIDERATIONS**

### **5.1. Sample Size Considerations**

Part C: Up to 50 pediatric subjects who are 4 to 17 years of age with SCD will be enrolled. For the primary efficacy endpoint, change from baseline in TAMM TCD velocity at Week 48, a sample size of 30 subjects achieves greater than 95% power to detect a mean difference of 15 cm/sec with an estimated sample standard deviation of 22 cm/sec using a paired t-test (2-sided) with a significance level (alpha) of 0.10.

### **5.2. Handling of Missing or Partial Dates**

#### **5.2.1. Missing Start and Stop Dates for Prior and Concomitant Medication**

For missing start day only: day will be imputed as the first day of the month (i.e., 1) with the following exception: If the partial date falls in the same month and year as the treatment start date then the concomitant medication start date will be imputed as the treatment start date.

For missing start day and month: day and month will be imputed as the first day of the year (i.e., 1 January) with the following exception: If the partial date falls in the same year as the treatment start date then the concomitant medication start date will be imputed as the treatment start date.

For missing stop day only: day only will be imputed as the last day of the month (i.e., 28, 29, 30, or 31).

For missing stop day and month: day and month will be imputed as the last day of the year (i.e., 31 December).

#### **5.2.2. Missing Start and Stop Dates for Adverse Events**

For missing start day only: day will be imputed as the first day of the month (i.e., 1) with the following exception: If the partial date falls in the same month and year as the treatment start date then the adverse event start date will be imputed as the treatment start date.

For missing stop day only: day only will be imputed as the last day of the month (i.e., 28, 29, 30, or 31).

## **6. ANALYSIS POPULATIONS**

### **6.1. Efficacy Evaluable Population**

All subjects who received at least one dose of study drug will be included in the Efficacy Evaluable population (EE). The EE population will be the primary population for the efficacy analyses.

### **6.2. Safety Population**

The Safety Population is defined as all subjects who receive at least one dose of study drug. This population will be used in the assessment and reporting of safety data.

### **6.3. PK Population**

All subjects who receive any amount of study drug and who provide PK data from at least one post dose sample in plasma will be included in the PK population. Additional details are provided in a separate plan.

## **7. STATISTICAL METHODS**

Statistical analyses will be performed using SAS® Version 9.4 or higher.

Data summaries will be presented as: 4-11 years, 12-17 years and overall (4-17 years) age groups.

Continuous variables will be descriptively summarized using number of subjects (n), mean, standard deviation (SD), median, quartiles, minimum, maximum, and, as appropriate, 95% confidence intervals. Categorical variables will be descriptively summarized by presenting the number (frequency) and percentage in each category.

### **7.1. Subject Disposition, Demographic and Baseline Characteristics**

#### **7.1.1. Subject Disposition**

Subject disposition will be presented in terms of the numbers and percentages of subjects who completed the treatment and discontinued from treatment. The reasons for early treatment discontinuation will be presented. Similar results will be presented for subjects who discontinue study.

#### **7.1.2. Demographic and Baseline Characteristics**

The demographic variables collected in this study include age (years) at Screening, sex, race, and ethnicity and will be summarized descriptively. Height (cm), weight (kg) and BMI (kg/m^2) at Screening will be presented using descriptive statistics. Subjects who record more than one race will be grouped into a single category denoted as multi-racial.

#### **7.1.3. Baseline Sickle Cell Disease Characteristics**

Number of VOCs including the number of VOCs requiring hospitalization and the number of blood transfusion during the previous 12 months will be summarized categorically.

Additional summaries including the number and percentage of subjects who currently use HU, who have each genotype (HbSS or HbS β thal) and who experienced a sickle cell complication prior to study enrollment will be presented. Baseline lab values including Hb, HbF, reticulocyte count and Baseline TCD will be summarized using descriptive statistics.

#### **7.1.4. Medical History Excluding Sickle Cell History**

Medical history excluding sickle cell history will be summarized by System Organ Class (SOC) and Preferred Term (PT) according to Medical Dictionary for Regulatory Activities (MedDRA), coding dictionary (current version).

## 7.2. Efficacy Analysis

Efficacy data will be summarized using the EE population.

The primary endpoint for Part C is change from baseline to 48 weeks in cerebral blood flow as measured by the TAMM TCD velocity.

TCD flow velocity will be summarized descriptively at Week 24 and Week 48 for observed values and absolute changes. TCD is presented as TCD (non-imaging) in the summary table. TCDi (imaging) has been normalized to TCD (non-imaging) by adding 15 cm/sec.

The proportion of subjects with normal TCD flow velocity (< 170 cm/sec by nonimaging TCD or < 155 cm/sec by TCDi) at 48 weeks will be summarized descriptively for the overall population and by Baseline TCD category (Normal, Conditional).

Hb response, defined as an increase in Hb > 1 g/dL, will be summarized descriptively at Week 24 and Week 48. Subjects who drop-out early or do not have a Week 24 or Week 48 visit, are not included in the analysis for Hb response at each of the respective visits. Additional response assessment at each visit will be summarized descriptively. No missing data imputation or adjustment for RBC transfusion will be performed for this endpoint.

Additionally, Hb response at Week 24 and Week 48 will be summarized using the treated population. All subjects treated will be included in the denominator for Hb response.

For subjects who have had a Hb response at least 1 visit, the time to the first response will be summarized descriptively.

Hematology parameters (hemoglobin, reticulocyte count, indirect bilirubin, and LDH) and in addition to each visit for observed values and changes (absolute and percent) from baseline using appropriate descriptive statistics. If indirect bilirubin is missing and direct and total bilirubin are collected, indirect can be calculated as:

$$\text{Indirect Bilirubin} = \text{Total Bilirubin} - \text{Direct Bilirubin}.$$

To evaluate the effect of voxelotor on the incidence of stroke and vaso-occlusive crisis (VOC), the annualized incidence rate will be summarized and 95% CI provided.

Efficacy assessment will be summarized by subgroups defined by subjects' sex, baseline HU use, and 4-11 age group (4 to 7 years and 8 to 11 years). Efficacy assessments to be summarized by subgroup include Hb response and change from baseline for hematology parameters and TCD flow velocity.

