2.3. Part C (Multiple Dose)

2.3.1. Primary Objective

- To evaluate the effect of voxelotor on cerebral hemodynamics in pediatric participants with SCD with elevated or conditional TCD flow velocity as assessed by TCD ultrasonography

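### Part C plans no TCD-change summary for the children its primary objective names, so the overall and 4–11 means may not estimate the effect in that group

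*SAP*

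**What the plan says.** - **Objective.** Protocol 2.3.1 directs the primary objective at "pediatric participants with SCD with elevated or conditional TCD flow velocity as assessed by TCD ultrasonography". The Part C SAP, 2.2.1, repeats this for "pediatric subjects with SCD with elevated or conditional TCD flow velocity as assessed by TCD ultrasonography". Protocol 1.3 gives the non-imaging bands: normal below 140 cm/sec, elevated 140–169, conditional 170–199.
- **Endpoint.** Part C SAP 3.1.1, matching Protocol 3.9.3.1, sets no velocity limit: "Change from baseline to 48 weeks in cerebral blood flow as measured by the TAMM TCD velocity".
- **Analysis.** Part C SAP 7.2 states: "TCD flow velocity will be summarized descriptively at Week 24 and Week 48 for observed values and absolute changes". It uses the Efficacy Evaluable population, which Section 6.1 defines as everyone dosed. Section 7 sets the columns: "Data summaries will be presented as: 4-11 years, 12-17 years and overall (4-17 years) age groups". Section 7.2 adds subgroups by sex, baseline hydroxyurea use, and ages 4–7 and 8–11. Baseline TCD is not among them.
- **Who is enrolled.** Protocol 1.3 says Part C takes children in the normal range too. Protocol 3.1.3 requires at least 30 of up to 50 at 140 to <200, and at least 20 aged 4–11. Inclusion criterion 10 applies the 140 floor only to ages 12–17.
- **Where baseline TCD is used.** Part C SAP 7.1.3 describes it as a baseline characteristic. Section 7.2 uses two baseline categories, Normal and Conditional, but only for the proportion with normal velocity at Week 48.

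**The concern.** The objective names one population and the analysis describes another. Children below 140 cm/sec are enrolled deliberately and are counted in the overall and 4–11 columns. Those means therefore depend partly on how many such children happened to enrol. If their TCD change differs from that of children at 140 to <200, neither column estimates the effect the objective asks about. The 12–17 column is a fair approximation for adolescents because of the entry floor.

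The two age columns also come from different TCD entry rules, so a difference between them may partly reflect baseline velocity and not age. A reader of the planned tables would have no overall or 4–11 estimate for the group named in the primary objective.

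**Working it through.** **1. The plan's own figure.** Part C SAP 5.1 gives n = 30, mean difference 15 cm/sec, SD 22, a paired t-test and two-sided alpha 0.10. The noncentrality is (15/22) × √30 = 3.73 on 29 degrees of freedom, and the exact power is 97.7%. The claim of more than 95% reproduces. The 30 equals the minimum quota at 140 to <200, so on these inputs the design supports a summary restricted to that group.

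**2. How many may lie outside the group.** The maximum is 50 − 30 = 20 of 50 (40%). The optional 20 extra participants must all be at 140 to <170, so with expansion the maximum is 20 of 70 (29%). Because of inclusion criterion 10, essentially all of these would be aged 4–11. There are two small exceptions. An adolescent who qualifies on one value could average below 140 if an unscheduled pre-dose value is included. A single value of 200 or more is not excluded either, because exclusion criterion 3 requires two.

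**3. Effect on the means.** Assume a change of −15 cm/sec in the target group (the SAP 5.1 figure, which that section does not tie to this group) and a change of e outside it. The documents give no value for e. The mean is (n₁ × −15 + n₂ × e)/(n₁ + n₂).

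| Column (target / outside) | e = 0 | e = −5 | e = −10 | e = −15 |
|---|---|---|---|---|
| Overall, 30 / 20 | −9.0 | −11.0 | −13.0 | −15.0 |
| Overall, 40 / 10 | −12.0 | −13.0 | −14.0 | −15.0 |
| Overall after expansion, 50 / 20 | −10.7 | −12.1 | −13.6 | −15.0 |
| Ages 4–11, 20 / 20 | −7.5 | −10.0 | −12.5 | −15.0 |

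The last row assumes that 40 of the 50 are aged 4–11 and that all 20 outside the group are among them. The range for e is illustrative and not a bound. A rise of 5 outside the group would give (30 × −15 + 20 × 5)/50 = −7. The permitted extreme, which is not an expectation, is that 30 adolescents fill the TCD quota and all 20 children aged 4–11 are below 140. The 4–11 column would then hold no child from the objective's group.

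**4. Precision of a restricted summary.** The 95% half-width is t(0.975, n − 1) × SD/√n.
- n = 30, SD 22: 8.2 cm/sec.
- n = 50, SD 22: 6.3 (6.25 before rounding).
- n = 50, 30/20 mix at e = 0: SD = √(22² + [30 × 6² + 20 × 9²]/49) = 23.2, half-width 6.6.
- n = 20 (for example, 20 qualifying at ages 4–11), SD 22: 10.3.

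All of these assume complete Week 48 TCD data.

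**5. Whether another planned output fills the gap.** The Week 48 proportion is a different endpoint. Its baseline categories have no stated cut-offs and no Elevated category. If Normal there means below 170, as in the outcome definition in the same sentence, it pools 140–169 with below 140. The baseline TCD description in 7.1.3 would show an imbalance between the age columns, but not the change in the target group.

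**The case against.** The strongest reply is that the SAP follows the protocol. The protocol endpoint is unrestricted, and Protocol 10.3 asks for Part C by age group. Part C is single-arm and descriptive, and Section 7.2 plans no test or decision rule on TCD. Protocol 10.3.3 also calls for listings of TCD velocity, so the subset could be worked out later. All of this stands. It makes the point a mismatch between objective and endpoint, with a missing table and no lost information. It does not supply the estimate, and a subset derived from listings after the fact would not be pre-specified.

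A reader might infer several stronger things that the documents do not support:
- *That the overall and 4–11 columns certainly miss the objective's effect.* No document gives the change in children below 140. If it equals the change inside the group, nothing shifts. The 20 of 50 is a maximum and not a forecast.
- *That the age columns differ in velocity by design.* Only the entry rules differ. Protocol 1.1 reports higher cerebral velocity in young children with the disease.
- *That the SAP definitely merges 140–169 into Normal.* That is an inference, since no baseline cut-offs are given.
- *That the sample size is wrong.* It reproduces.

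A restricted summary also has a weakness. Protocol Appendix 5 schedules TCD before dosing only at Screening, so the qualifying value is normally also the baseline. Selecting on it exposes the subset to regression to the mean more than the all-treated mean, and there is no control arm. The documents give no between-visit correlation from which to size this. That is a reason to report both summaries together, not to omit the restricted one.

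**Conclusion.** The point holds, and the plan should be amended. The Part C SAP has no summary of TCD change for the population in its own primary objective, and the overall and 4–11 means may not estimate the effect there. At the design maximum of 20 of 50 outside the group, a 15 cm/sec fall inside and a 0–15 fall outside give an overall mean from −9 to −15. The possible shift is therefore 0 to 6 cm/sec. In the 4–11 column with 20 of 40 outside, it is 0 to 7.5. These sizes rest on an assumed change outside the group and on the SAP's 15 cm/sec holding inside it. The actual share outside may be smaller than the maximum.

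**What to change.** In Part C SAP 7.2:

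1. Add the Week 24 and Week 48 TCD change for Efficacy Evaluable participants with baseline ≥140 and <200 cm/sec on the non-imaging scale (after the SAP's +15 conversion of imaging values), overall and at ages 4–11. Report n, mean, SD and 95% CI. Section 7 already allows for "as appropriate, 95% confidence intervals". Identify this as the summary matching the objective's population.
2. Keep the all-treated summary of the protocol endpoint beside it.
3. State the TCD baseline: the Screening value, averaged with any unscheduled pre-dose value. The averaging rule in Section 4 is written for endpoints measured at both Screening and Day 1, and Part C TCD has no scheduled Day 1 measurement. The quota applies at Screening, so the number qualifying on this baseline could differ slightly from the quota count.
4. Show n and change by band: <140, 140 to <170, 170 to <200, and ≥200 if any. Define the cut-offs for the baseline categories used with the Week 48 proportion.
5. State with the restricted result that part of any fall may be regression to the mean and that there is no control arm.

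The cost is some SAP wording and a few table rows from data already collected. The restricted interval is wider: a 95% half-width of about 8.2 cm/sec at n = 30 against 6.3–6.6 at n = 50, and about 10.3 if only 20 qualify at ages 4–11. Missing Week 48 values would widen it further, and some bands may be small.
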